## 6.2 Analysis of Images

The trial will acquire at least 115 matched images for analysis by three independent readers who are experienced radiologists and were not involved in the cases during which these images were captured. Sample images of IVUS and OCT will be reviewed prior to the image assessment to create a consistent nomenclature for the readers when identifying different tissue types with both imaging modalities and standardize the image review process. The images will be anonymized and given a unique identification number prior to assessment by the readers. Since the presentation of IVUS and OCT images are visibly different, the readers cannot be blinded as to which imaging device used to generate the image, but the images will

be provided in a random sequence so that the reader cannot match a specific IVUS image to a specific OCT image at the time of the review.

The readers will view the images and rank each for clarity (using a visual analogue scale or VAS) and identification of vessel morphology and disease pre- and post-procedure.

Qualitative interpretation of OCT and IVUS images will be ranked as follows:  
on) for:

- Layered structure – intima, media, external elastic lamina and adventitia (ranked as 1- clear differentiation of the vessel wall layers, 2- differentiation of at least three vessel wall layers, 3- differentiation of at least two vessel wall layers, and 4- no differentiation of any vessel wall layer);
- Non-layered structure—presence of disease in the vessel structure (a 5-point VAS of 1- excellent histology-like image quality to 5- unacceptably poor image quality);
- Abnormal physiology—dissection/tissue flap/false lumen, thrombus, calcium (a 5-point VAS of 1- excellent histology-like image quality to 5- unacceptably poor image quality);
- Bifurcation of the vessel (1- excellent image, 2- acceptable image, 3- unacceptably poor image quality); and
- Frequency of artifacts (ranked as 1- no artifacts, 2- tolerable/not limiting diagnostic image quality, 3- intense and limits diagnostic image quality).

The results of all readings of both imaging modalities will be used for intrareader and interreader comparison to evaluate the reproducibility and reliability of the respective imaging modality.

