## **5.2. Sample Size Estimate**

When the sample size is 108 images of both the OCT and IVUS catheters, a two group 0.05 one-sided matched t-test will have 90% power to reject the null hypothesis that the test (OCT) and standard (IVUS) are not equivalent in favor of the alternative hypothesis that the two groups are equivalent. To obtain 108 vessel segment images at five images per subject, 22 subjects would be needed; however, recognizing that some images (~ 5%) may be of poor quality and illegible, 25 subjects should be enrolled and 115 images evaluated.

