## **5.3. Study Endpoints**

Primary efficacy endpoint is met when OCT imaging has the equivalent or higher ranking of IVUS imaging of the visualization of vessel morphology and disease for:

- Layered structure – intima, media, external elastic lamina, and adventitia;
- Non-layered structure—presence of disease in the vessel structure;
- Abnormal physiology—dissection/tissue flap/false lumen, thrombus, calcium;
- Bifurcation of the vessel; and
- Frequency of artifacts.

Secondary efficacy endpoint is met when OCT imaging has the equivalent dimensions of vessel diameter and total luminal area as that determined with IVUS imaging.

Primary safety endpoint is freedom from diagnostic imaging procedure-related and device-associated adverse events, as reported by the physician.

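### Bifurcation and abnormal findings are graded on every image with no 'not present' code and no analysis rule, so for these two primary components the 90% power at 108 pairs and the 5% error rate are not secured

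*Combined protocol and SAP*

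**What the plan says.** Section 6.2 has the readers rate each image. Bifurcation is graded on three points: "Bifurcation of the vessel (1- excellent image, 2- acceptable image, 3- unacceptably poor image quality". The item "Abnormal physiology—dissection/tissue flap/false lumen, thrombus, calcium" is graded on five points, from excellent to unacceptably poor image quality. Neither scale has a level for a frame in which the feature is absent. The artifact scale in the same list does have a none-present level, as its grade 1.

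Both items are in the section 5.3 list: "Primary efficacy endpoint is met when OCT imaging has the equivalent or higher ranking of IVUS imaging", followed by the five components.

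Section 5.2 does not tie its calculation to any one component. It counts every image, as its opening words show: "When the sample size is 108 images of both the OCT and IVUS catheters". The claim it seeks to establish is worded "in favor of the alternative hypothesis that the two groups are equivalent", by a one-sided matched t-test at 0.05 with power set at 90%. The only allowance for lost images is "recognizing that some images (~ 5%) may be of poor quality and illegible". Section 6.3 averages all readings of all readers and does not mention frames that lack a feature. Section 6.1 takes images from a pullback of 5 to 10 cm, and no rule selects frames that contain a bifurcation or an abnormality.

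**The concern.** A reader shown a frame without a bifurcation has no defined answer, and the analyst has no defined handling. Two things can happen.

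- **The frame is graded anyway.** The grade then says nothing about how well the modality shows a bifurcation. If such frames score alike on average, the mean OCT deficit becomes prevalence times the true deficit. In a superiority trial that dilution would be conservative. Here the claim is equivalence, so dilution helps the claim succeed.
- **The frame is left blank.** The number of pairs falls below 108. Pairs in which only one modality shows the feature drop out, and those are the pairs that say most about a difference between modalities.

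Section 6.2 also says readers cannot be blinded to modality. Grades or omissions on absent-feature frames could therefore differ by modality and bias the comparison in either direction.

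**Working it through.** **Inputs from section 5.2:** 108 pairs, one-sided 0.05, matched t-test, 90% power, five images per subject, about 5% illegible, 115 images evaluated. **Not stated:** the margin, the SD of paired differences, the true difference, and the share f of pairs in which the feature is present. I assume a true difference of zero for power, and I vary f. Like section 5.2, I treat pairs as independent.

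**Step 1: the plan's own figures.** "To obtain 108 vessel segment images at five images per subject, 22 subjects would be needed": 108/5 = 21.6, so 22, which agrees. Allowing 5% loss, 108/0.95 = 113.7, so 114 against the stated 115, which is close enough. The slack is 115 − 108 = 7 images, already assigned to illegibility. The 108 cannot be reproduced without a margin and SD, but their ratio can be back-solved:

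- One-sided (non-inferiority): (1.645 + 1.282)/√108 = 0.282; exact t, 0.283 SD.
- Two one-sided tests (equivalence): (1.645 + 1.645)/√108 = 0.317; exact t, 0.319 SD.

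Both are shown because section 5.2 states an equivalence hypothesis and section 5.3 accepts equivalent or higher.

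**Step 2: absent frames dropped.** Pairs analysed = 108f. Power is from the exact t calculation at the margins above.

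| Presence f | Pairs | One-sided | Two one-sided |
|---|---|---|---|
| 100% | 108 | 90% | 90% |
| 75% | 81 | 81% | 77% |
| 50% | 54 | 66% | 50% |
| 20% | 22 | 36% | 3% |

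Power stays at 80% or more only with at least 79 pairs (79/108 = 73%) one-sided, or 86 pairs (86/108 = 80%) for two one-sided tests.

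**Step 3: absent frames graded, with mean difference zero.** Work in units of the SD of differences in feature-present pairs. Let the true OCT deficit there be 0.283, equal to the one-sided margin. The observed mean deficit is f × 0.283. Approximately, P(pass) = Φ[(M − 0.283f)√108/S − 1.66], where M is the margin, S the SD over all 108 pairs, and 1.66 the t critical value. At f = 0.50, 0.283f = 0.142:

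- Absent frames noisy, S = 1, M = 0.283: Φ(1.47 − 1.66) ≈ 43%.
- Absent frames exact ties, S = √(0.5 × (1 + 0.283²) − 0.142²) = 0.72, M = 0.283: Φ(2.04 − 1.66) ≈ 65%.
- Exact ties, with the margin rescaled to the SD of all pairs, M = 0.283 × 0.72 = 0.204: the approximation gives about 23%, simulation 24%. The deficit of 0.283 now exceeds the margin, yet passes this often.

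At f = 0.75, simulation gives 18%, 22% and 12% for the same three cases. The nominal 5% therefore becomes 12-22% at 75% presence and 24-65% at 50%. For two one-sided tests with the margin fixed at 0.319, the ranges are 20-25% and 49-73%; the lower figure has noisy absent frames and the upper has exact ties.

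**The case against.** The strongest reply is that nothing in the documents fixes the size. Prevalence is not given, and the two items may differ: subjects have peripheral arterial disease, and calcium counts as an abnormal finding, so that item may be gradable on most frames even if bifurcation is not. A reader might infer that the analysed number must fall far below 108. The documents do not support that; if about three quarters of pairs show the feature, one-sided power stays near 80%.

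A reader might also infer that a clear OCT deficit would usually pass. Take a 0.5-grade deficit, an assumed SD of 0.8 and a margin of 0.283 × 0.8 = 0.227 grade. Simulation does give pass rates of 50% and 90% at 30% and 20% presence, but only with exact ties and a margin fixed on the feature-present SD. With noisy absent frames the rates are about 25% and 48%, and with the margin scaled to all 108 pairs about 5% and 16%. Nor do the documents show that absent frames tie: readers know the modality and see unmatched images in random order, so bias could run either way.

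Two textual cautions also stand. The sentence introducing the scales in 6.2 is damaged in the available text, so a general scoring instruction may be lost. The planned review of sample images could settle how readers treat absent features. Neither would supply an analysis rule in 6.3 or an allowance in 5.2, and both scales are legible and have no absent level.

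**Conclusion.** The gap is real and should be closed before reading starts, because absence cannot be recovered from a forced grade. Two primary components have no 'not present' code and no analysis rule, so the stated 90% power describes them only if the feature is in essentially every pair. The consequence is conditional. At 50% presence, power is 66% (one-sided) or 50% (two one-sided tests) if absent frames are dropped. If they are graded with no average difference, the one-sided false pass rate is about 24-65% instead of 5%. At 75% presence the figures are 81% or 77%, and 12-22%. All rest on a margin back-solved from section 5.2, independent pairs and an assumed prevalence. They show what the plan leaves open and do not predict what this trial would find.

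**What to change.** 1. In 6.2, add a 'not present' code to the bifurcation and abnormal-physiology scales. Record it beside the quality grade, so that a pair later judged feature-present still has a grade from both modalities.
2. Decide presence once per matched pair, by a prespecified rule that does not depend on the grade of the modality being scored. One example is a majority of the three existing readers, taken over both modalities' readings of the pair.
3. In 6.3, analyse these two components only in feature-present pairs, and keep pairs in which one modality does not show the feature. Use a worst-grade assignment to that modality only as a sensitivity analysis. As the main rule, it would penalise a modality that correctly shows nothing whenever the other is over-called.
4. In 5.2, state that 90% power at 108 pairs applies only to components gradable on every frame. Give the power for these two over a range of prevalence, with the margin and SD stated.

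The cost is one extra code on the reader form, a little more analysis, and less favourable stated power for two components. No extra subjects, images or readers are needed to make the change.

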### 6.3 Statistical Analyses

Statistical analyses will be carried out using StatView software (SAS Institute, Cary, NC). A  $p$  value  $< 0.05$  will be considered statistically significant. Matched Pairs  $t$ -Test will be performed to compare means and on paired samples to compare procedural data and complications associated with the imaging techniques. The mean values of the results of all readings of all readers will be calculated for comparison of image quality. Fisher's Exact Test will be used to compare proportions. The Mann-Whitney-Wilcoxon test will be applied for statistical comparison of the results for OCT and IVUS imaging. Interreader and intrareader reproducibility will be calculated by intraclass correlation (ICC) analysis in a two-way mixed model. Correlation of the mean values of the results of the quantitative measurements of all readers with both imaging modalities will be calculated as Pearson correlation coefficient.

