## **5. INVESTIGATIONAL PLAN**

### **5.1. Study Design Overview**

The purpose of this is a study to collect images of the same vessel segments using both the IVUS and OCT systems so that a comparison can be made of the two imaging modalities. IVUS and OCT images will be captured at identical positions within vessel segments. Continuous imaging will occur as the catheters are moved from distal to proximal endpoints established with a radiopaque marking tape attached to the subject's leg.

The trial will enroll up to 25 subjects diagnosed with peripheral arterial disease of the lower extremities, with the goal to acquire at least 115 matched images for analysis.

The images will be anonymized and given a unique identification prior to assessment by three radiologists (readers) for review. The readers will review the images and rank each for image clarity (using a visual analogue scale or VAS) and identification of vessel morphology and disease pre- and post-procedure.

The inclusion criteria for subjects are:

1. Subject is an adult ( $\geq 18$  years old); and
2. With suspected vascular disease that might be a candidate for IVUS; and
3. Reference vessel lumen is acceptable for use of the Pantheris and IVUS catheters as per visual angiographic estimation.
4. Successful diagnostic imaging and removal of the IVUS catheter with no adverse events.

The exclusion criteria are:

1. Subject, if female, is pregnant or breast feeding; or
2. Subject is unwilling to give informed consent.

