## 7. SAFETY AND DEVICE MALFUNCTION REPORTING

### 7.1. Safety Reporting

Incidence and severity of procedure-related and device-related adverse events (*e.g.*, vessel spasm, thrombosis, distal embolism, *etc.*) will be evaluated following each scan and documented over the course of the study. All adverse events (AEs) will be required to be completely documented through Avinger's complaint handling process..

The following events will be considered to be serious adverse events (SAEs) and must be reported to the Sponsor by telephone, fax and/or email. These events must be reported whether or not the Investigator believes they are related to study procedures, activities or device:

- Death;
- Life-threatening event;
- Disability – significant, persistent, or permanent change, impairment, or damage or disruption in the subject's body function/structure, physical activities or quality of life;
- Necessitate immediate medical or surgical intervention to:
  - Preclude permanent impairment of a body function or permanent damage to a body structure
  - Relieve unanticipated temporary impairment or damage; or
- Prolongation of a hospitalization.

It is the responsibility of the Investigator to inform their Institutional Review Board (IRB) of serious adverse events as required by their IRB's procedures and in conformance with local regulatory requirements.

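### Section 6.3 compares complications by a matched t-test that is undefined with no events, the primary safety endpoint has no estimate or interval, and inclusion criterion 4 makes any device comparison of complications one-directional

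*Combined protocol and SAP*

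**What the plan says.** Section 5.3 sets the safety objective: "Primary safety endpoint is freedom from diagnostic imaging procedure-related and device-associated adverse events, as reported by the physician". It gives no rate, threshold, unit of analysis or population.

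Section 6.3 mentions complications once. A matched-pairs t-test "will be performed to compare means and on paired samples to compare procedural data and complications associated with the imaging techniques". The same paragraph adds that "Fisher's Exact Test will be used to compare proportions", without saying which proportions, and that a p value below 0.05 "will be considered statistically significant", without saying one-sided or two-sided.

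Section 7.1 says that related adverse events "will be evaluated following each scan and documented over the course of the study". That covers collection and describes no analysis.

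Two design statements decide who can contribute an event. Inclusion criterion 4 in 5.1 requires "Successful diagnostic imaging and removal of the IVUS catheter with no adverse events". Sections 5.4 and 6.1 count a subject as enrolled only when the OCT (Pantheris) catheter goes in, after the IVUS run and after consent. On size, 5.1 says "The trial will enroll up to 25 subjects diagnosed with peripheral arterial disease of the lower extremities".

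**The concern.** There are three linked problems.

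1. The one method tied by name to complications is a test of mean differences applied to a rare binary outcome. It cannot be computed when no event occurs, which is the result the safety endpoint describes as success.
2. The primary safety endpoint is about freedom from events. A between-device test does not estimate that, so a primary endpoint has no stated estimator and no measure of precision.
3. Subjects with an IVUS event fail criterion 4 and never reach OCT insertion. Among enrolled subjects the IVUS count is zero by construction, so the comparison can show only that OCT is the same or worse.

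At stake are an undefined result if safety is perfect, a possibly spurious finding against the sponsor's own device if a few OCT events occur, and a freedom-from-event figure that leaves out harm from the first of the two imaging procedures.

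**Working it through.** **The plan's own figure.** The documents state no number for the safety analysis. The sample size in 5.2 ("a two group 0.05 one-sided matched t-test will have 90% power to reject the null hypothesis") concerns image equivalence and does not bear on safety.

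**Inputs.** n = 25 subjects (5.1). Before the allowance for poor images, 5.2 gives 108/5 = 21.6, rounded up to 22. IVUS events among enrolled subjects = 0 (criterion 4). The event rate is not given; I assume 2% to 20% per subject.

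**Step 1: no events.** All paired differences are 0, so their mean and SD are 0 and t = 0/0. With IVUS at zero, the chance of this is (1 − p)^25:

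| Assumed OCT rate | Chance that t is undefined |
|---|---|
| 2% | 60% |
| 5% | 28% |
| 10% | 7% |

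**Step 2: k OCT events, no IVUS events.** The differences are k ones and n − k zeros. Their mean is k/n and their variance is k(n − k)/[n(n − 1)], so t = √[(n − 1)k/(n − k)] on n − 1 degrees of freedom. For k = 4, t = √(24 × 4/21) = 2.138. The two-sided exact McNemar p is 2 × 0.5^k. Fisher treats the two sets of 25 as independent.

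| k vs 0, n = 25 | t | t-test p | McNemar p | Fisher p |
|---|---|---|---|---|
| 3 | 1.809 | 0.083 | 0.250 | 0.235 |
| 4 | 2.138 | 0.043 | 0.125 | 0.110 |
| 5 | 2.449 | 0.022 | 0.063 | 0.050 (0.0502) |
| 6 | 2.753 | 0.011 | 0.031 | 0.022 |

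At two-sided 0.05 the t-test crosses at 4 events; McNemar and Fisher cross at 6.

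**Step 3: effect of the selection.** Suppose OCT and IVUS have the same true rate before selection, and passing the IVUS run does not change a subject's OCT risk. The chance of a nominally significant result against OCT is then P(X ≥ 4) for the t-test and P(X ≥ 6) for McNemar, with X binomial(25, p):

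| Common rate p | t-test | Exact McNemar |
|---|---|---|
| 5% | 3.4% | 0.1% |
| 10% | 23.6% | 3.3% |
| 15% | 52.9% | 16% |
| 20% | 77% | 38% |

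An exact test lowers these chances but does not remove the bias.

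**Step 4: what the endpoint would yield if estimated directly.** With no events the lower Clopper-Pearson 95% limit is 0.025^(1/n).

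| Events / n | Event-free | 95% interval |
|---|---|---|
| 0/25 | 100% | 86.3% to 100% |
| 1/25 | 96% | 79.6% to 99.9% |
| 2/25 | 92% | 74.0% to 99.0% |
| 0/22 | 100% | 84.6% to 100% |

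The interval exists at every count, including zero. The population matters too. If 25 enrolled subjects have no event but one further consented subject had an IVUS event, the figure is 25/26 = 96.2% (80.4% to 99.9%) rather than 100%.

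**The case against.** **Fisher's exact test is in the same paragraph.** An adverse-event rate is a proportion, and Fisher can be computed with no events. Section 7.1 also implies a descriptive count, so 0/25 would presumably be reported. This stands to the extent that the t-test cannot be called the only safety analysis in 6.3; it is the only one that names complications. Fisher is assigned to no endpoint, treats paired observations as independent, and compares devices without estimating freedom from events.

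**The t-test may be said to exaggerate significance.** A reader might infer this from 0.043 against 0.125. The comparison does not show it, because exact McNemar is conservative at this size. With equal, independent rates and no selection, enumeration at n=25 gives a two-sided type I error for the t-test of 0.2%, 2.0%, 4.7%, 4.8% and 4.5% at rates of 2%, 5%, 10%, 15% and 20%. McNemar gives 0.0%, 0.1%, 0.7%, 1.4% and 1.9%. The t-test does not exceed 5%, so general inflation is not supported. The high rejection rates in step 3 come from the selection.

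**Section 5.3 does not call the endpoint a proportion.** Correct. Reading freedom from events as a per-subject yes/no outcome is an inference, though the natural one, and it is a reason to state the unit.

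**IVUS events may not be exactly zero.** An IVUS-related event recognised only after OCT insertion, or an enrolment in breach of criterion 4, could still appear. This softens the zero slightly and leaves the direction of the bias unchanged.

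**Conclusion.** The point holds in this form. The t-test named for complications is undefined when there are no events, with a chance of 60%, 28% or 7% at assumed OCT rates of 2%, 5% or 10%. The primary safety endpoint has no stated estimate, interval or population. Any test of OCT against IVUS complications in enrolled subjects is one-directional by design: 4 OCT events suffice for the t-test and 6 for exact McNemar, even with equal unselected rates.

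The undefined statistic, the missing estimator and the selection follow from the text. The probabilities rest on assumed event rates, n=25, two-sided 0.05 and, in step 3, OCT risk unrelated to having passed IVUS. If 6.3 intends a one-sided 0.05, the thresholds fall to 3 events for the t-test (p=0.042) and 5 for McNemar (p=0.031).

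The documents do not support two stronger readings: that 6.3 contains no other test applicable to event rates, and that the t-test has inflated type I error in general. Nor would substituting McNemar make the device comparison valid. This should be corrected before analysis. Safety data are still collected, so a sound analysis remains possible.

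**What to change.** In 6.3, remove complications from the matched t-test. Add that the primary safety endpoint is the proportion of subjects free of related adverse events, with a Clopper-Pearson 95% interval.

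State the unit (subject) and the population. The population should count consented subjects who had an IVUS event and so did not go on to OCT, alongside enrolled subjects. Show events by the imaging step after which they were recorded, with the denominator for each step.

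If OCT and IVUS are set side by side, present counts only, label the comparison descriptive, and say that criterion 4 removes IVUS events from the enrolled group. State which proportions Fisher's test is meant for, or that it does not apply to complications.

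The cost is text in 6.3, a population definition, and a little more tabulation, including a record of events in consented subjects who were not enrolled. No extra subjects or procedures are needed. The downside is that there will be no formal between-device p value for complications.

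### Section 6.3 does not carry through the matched equivalence test of 5.2: it applies an unpaired test of difference, and no margin is stated, so equivalence cannot be shown

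*Combined protocol and SAP*

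**What the plan says.** Section 5.1 has both devices image the same positions in the same vessel segments, and section 6.2 calls for at least 115 matched images scored by three readers.

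Section 5.2 arrives at 108 images per modality, at five per subject, on the basis that "a two group 0.05 one-sided matched t-test will have 90% power to reject the null hypothesis". The hypothesis rejected is "the null hypothesis that the test (OCT) and standard (IVUS) are not equivalent in favor of the alternative hypothesis" of equivalence.

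Section 5.3 sets the success criteria. "Primary efficacy endpoint is met when OCT imaging has the equivalent or higher ranking of IVUS imaging" on five listed features. "Secondary efficacy endpoint is met when OCT imaging has the equivalent dimensions of vessel diameter and total luminal area" compared with IVUS.

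Section 6.3 gives the analyses, with significance at p below 0.05 and no sidedness:
- a matched-pairs t-test, which "will be performed to compare means and on paired samples to compare procedural data and complications associated with the imaging techniques";
- an average over every reading by each of the three readers, as the basis for judging image quality;
- Fisher's exact test for proportions;
- "The Mann-Whitney-Wilcoxon test will be applied for statistical comparison of the results for OCT and IVUS imaging";
- for dimensions, the correlation of the "quantitative measurements of all readers with both imaging modalities will be calculated as Pearson correlation coefficient".

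Section 6.2 scores the five features on 3-, 4- or 5-level scales. On every one of them 1 is best.

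**The concern.** The test that justified the sample size and the test named for comparing the two modalities differ in two ways. The first is paired with an equivalence null. The second treats the two sets of images as independent and has a null of no difference. Section 6.3 does not say which analysis decides either efficacy endpoint.

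The missing margin is the more serious gap. Without a stated distance that counts as equivalent, no test result can support that word, and swapping Mann-Whitney for a paired rank test would not change this. A margin chosen after scores are seen would not be pre-specified.

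The unpaired test also works in an unhelpful direction. With positive correlation within pairs it is conservative for a difference, so it is less likely than a paired test to reveal that OCT is worse.

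**Working it through.** **1. The plan's own figure.** Section 5.2 gives one-sided alpha 0.05 (z = 1.645), power 90% (z = 1.282) and n = 108, but no margin, SD or expected difference. So 108 cannot be reproduced. Solving backwards with a true difference of zero:
- paired non-inferiority: (1.645 + 1.282)/√108 = 0.28 SD of the paired difference;
- paired equivalence by two one-sided tests: (1.645 + 1.645)/√108 = 0.32 SD of the paired difference;
- two independent groups of 108, one-sided: (1.645 + 1.282) × √(2/108) = 0.40 SD of a single image.

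The wording of 5.2 (both two-group and matched) does not settle which was meant, so 108 identifies no single margin. The counts around it are sound: 22 × 5 = 110 covers 108, and 108/0.95 = 114 agrees with the 115 images planned.

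**2. What the choice of test does.** The documents give no SD or correlation, so this is an illustration by simulation. Assumed: a normal latent score with variance 1, cut at −1.5, −0.5, 0.5 and 1.5 into five categories; 108 independent pairs; one reading per image; OCT truly worse by 0.28 SD of a single image; within-pair correlation 0.5. At that correlation the SD of a latent paired difference is √(2 × (1 − 0.5)) = 1, so 0.28 is the same in single-image and paired units. At other correlations the two units differ.

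| Share of trials non-significant | Mann-Whitney | Matched t |
|---|---|---|
| two-sided 0.05 | about 50–52% | about 24% |
| one-sided 0.05, as in 5.2 | about 34% | about 15% |

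On the same data the two tests reach different conclusions in about 28% of trials (two-sided) or 19% (one-sided). With no true difference, the two-sided Mann-Whitney test rejects in about 0.8% of trials instead of 5%.

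**3. Several images per subject.** Assumed: 22 subjects × 5 images, correlation 0.5, and a component shared by one subject's images of one modality, expressed as a share of each image's total variance.

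| Share | Two-sided matched-t size, clustering ignored |
|---|---|
| 0 | 5% |
| 0.10 | 13% |
| 0.15 | 17% |
| 0.30 | 27% |

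Using the matched t-test of 6.3 without a cluster adjustment is therefore not a full remedy.

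**4. Secondary endpoint.** Suppose every OCT diameter equals the IVUS diameter plus a constant c. Then Pearson r = 1 whatever c is. The only analysis that 6.3 ties by name to the quantitative measurements cannot detect such an offset, and so cannot establish equal dimensions.

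**The case against.** The plan does contain the parts of an equivalence analysis. Section 5.2 names a matched test with a non-equivalence null. Section 6.3 lists a matched-pairs t-test for means, and its next sentence averages all readings to compare image quality. This stands: a reader might infer that the plan has no paired test and no route to equivalence, and that goes too far. The route is begun in 5.2, but it has no margin and is not carried into 6.3.

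A reader might also infer that the sponsor will treat a non-significant p-value as equivalence. Nothing in the documents says so.

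Nor is it right that the five features have no combining rule. They form a list joined by *and*, which most naturally means that all five must pass. The fair criticism is that this is not explicit. The direction of scoring is settled by 6.2.

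Finally, every simulated percentage depends on assumptions, including sidedness: the half-of-trials figure is two-sided, while 5.2 is one-sided. The argument from the text needs none of these numbers.

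**Conclusion.** The concern holds and must be fixed before images are read. Followed as written, section 6.3 applies an unpaired test to position-matched data, leaves the deciding test unassigned, ignores repeated images within a subject, and has no margin for either efficacy endpoint. A significant result could show OCT to be better; nothing planned could show it to be equivalent.

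The defect itself rests on the text alone. Its size rests on the assumed correlation, category cuts, shift and variance shares. Under those, Mann-Whitney misses the deficit roughly twice as often as the matched t-test, on either choice of sidedness. It does not follow that 108 is too few: without a margin and an SD, the number can be neither confirmed nor faulted.

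**What to change.** Replace the Mann-Whitney sentence with one primary analysis, for example:

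> For each of the five features, the reader-averaged paired difference (OCT minus IVUS; lower is better) is computed at every location where the feature can be rated on both modalities. OCT is non-inferior on a feature if the upper one-sided 95% confidence limit of the mean difference, computed with the patient as cluster, lies below the pre-specified margin. The primary endpoint is met if all five features pass. A non-significant difference is not evidence of equivalence.

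The sponsor should also:
- state and justify a margin for each feature before images are read;
- say how locations without a given feature (bifurcation, dissection, thrombus) are handled;
- for the secondary endpoint, declare equivalence if the 90% confidence interval of the per-segment paired difference lies within pre-stated limits, for mean diameter and for luminal area. Section 6.1 derives these per target segment, so cluster by patient only where a patient has more than one. Keep Pearson as descriptive;
- use a paired method for OCT-versus-IVUS proportions at the same locations;
- align the 5.2 hypothesis with the *equivalent or higher* criterion of 5.3, give the margin and SD behind 108, and restate the 90% power for the clustered analysis.

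**Cost.** The margins must be defended, and power may fall. In the step 3 setting, take no true difference and a margin of 0.28 latent SD (0.27 scale points). Power per feature is then about 83% with no subject-by-modality component, and 65, 57 and 44% at shares of 0.10, 0.15 and 0.30. If all five must pass, 83% per feature gives 0.827⁵ = 39% jointly if the features are independent, and at most 83%. In return the false-pass rate stays near 5%, against 10, 13 and 18% at those three shares if clustering is ignored. No extra images or procedures are needed if the power is restated. Keeping 90% would need wider margins or more images, and section 5.1 limits enrolment to 25 subjects.
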